8.2.6 MRI IMAGING

Subjects will undergo MRI imaging at HealthPartners Neuroscience Center. Subjects will be screened for any contraindications for MRI. Subjects will undergo a protocol based on recommendation by Omniscent (o8t MR Acquisition Recommendations). We anticipate 15 minutes of scan run time using a 3T Siemens Skyra scanner and the following images will be obtained.

- High-resolution multi-scan directional diffusion scan, which is most similar to a diffusion tensor image (DTI) acquisition Specifically, diffusion weighted imaging with the following acquisition parameters will be used: 2 mm x 2 mm x 2 mm voxels, FOV = 25.6 cm, matrix = 128 mm x 128 mm, slice thickness = 2.0 mm, one non-zero b-value of b = 1000, 40 directions, and gap = 0.0 mm.
- 2) EPI BOLD rs-fMRI A resting-state fMRI as a T2-star EPI sequence, with 3 x 3 x 3-mm voxels, 128 volumes/run, a TE = 27ms, a TR = 2.8s, a field of view 256mm, a flip angle = 90°
- 3) Anatomical Scan –T1 Weighting

All images will be de-identified and uploaded to the infintome cloud-based server to be analyzed. Internal guidelines/best practices based on infinitome user manual will be developed for transfer, obtaining accounts, uploading of raw images and downloading of analyzed data.

This will be transferred to the Localite Neuro Navigator to help with target areas for TMS Treatment

8.2.7 CONNECTOMIC ANALYSIS

All subject images will be processed using the infinitome tool. This will be used to conduct a connectomic analysis to identify large scale brain networks.

The Infinitome tool creates a machine learning-based, subject specific version of the Human Connectome Project-Multimodal Parcellation (HCP-MMP1) atlas based upon diffusion tractography structural connectivity (Figure 3). All data uploaded to the cloud is de-identified. This novel method was created by training a machine learning model on 200 normal subjects by first processing T1 and DT images. An HCP-MMP1 atlas in NIFTI MNI space is then warped onto

each brain and the structural connectivity calculated between every pair of this atlas and a set of ROI containing 8 subcortical structures per hemisphere and the brainstem based on the streamlines which terminated within an ROI. To ensure this atlas is applicable to pathologically distorted brains, a machine-learning tool takes the individual's DTI or CSD tractography and locates every voxel and reassigns them to an area that fits more accurately with the structural connection to create a personalized adjusted atlas. The personalized patient atlas is used to subset the resting-state and CSD tractography data to create Structural and Functional connectivity matrices. When these matrices are compared to other individuals using machinelearning, an output of structural and functional anomaly matrices demonstrates the abnormal connectivity in this subject's brain (Figure 4). Abnormal connectivity is determined as a 3-sigma outlier for that correlation, after excluding the highest variance 1/3 of pairs, to further reduce the false discovery rate. Assignment of parcellations to various large-scale brain networks is based on several previous coordinate based meta-analysis and matching the HCP-MMP1 parcellations to the coordinates of the ALE in MNI space, which has been previously published (or in review presently) by our group.

Figure 4: Connectomic Analysis

[figure not shown]
[figure not shown]

Figure 3: Anomaly Matrix for LSBNs in Temporal Lobe

8.3 SAFETY AND OTHER ASSESSMENTS

8.3.1 TRANCRANIAL MAGNETIC STIMULATION ADULT SAFETY SCREEN (TASS)

Screening questionnaire to assess the safety of TMS prior to treatment. This will be conducted at visits 1 and 2.

8.4 ADVERSE EVENTS AND SERIOUS ADVERSE EVENTS

8.4.1 DEFINITION OF ADVERSE EVENTS (AE)

An adverse event is any symptom, sign, illness or experience which develops or worsens in severity during the course of the study. Intercurrent illnesses or injuries should be regarded as adverse events. Abnormal results of diagnostic procedures are considered to be adverse events if the abnormality:

- Results in study withdrawal.
- Is associated with clinical signs or symptoms.
- Leads to treatment or to further diagnostic tests.
- Is considered by the investigator to be of clinical significance.

8.4.2 DEFINITION OF SERIOUS ADVERSE EVENTS (SAE)

Adverse events are classified as either serious or non-serious. A serious adverse event is any event that results in:

- Death.
- Life-threatening situation.
- Hospitalization or prolongation of hospitalization.
- Disability or incapacitation.
- Other events determined by investigator to be medically significant in which subject's well-being is jeopardized (e.g. events that have high likelihood of escalating to the point of meeting criteria outlined above)

8.4.3 EXPECTEDNESS

PI will be responsible for determining whether an adverse event (AE) is expected or unexpected. An AE will be considered unexpected if the nature, severity, or frequency of the event is not consistent with the risk information previously described for the study intervention.

8.4.4 TIME PERIOD AND FREQUENCY FOR EVENT ASSESSMENT AND FOLLOW-UP

Upon consenting, a subject is considered to be a participant in the study, and until that person either withdraws or completes study, AEs and SAEs will be recorded. The investigational team will promptly report any AE/SAE as required per federal guidelines.

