1.3 SCHEDULE OF ACTIVITIES (SOA)

Table 1: Study Visit Schedule

Procedure	Screening	Baseline	Treatment	Follow-up	Early Withdrawal
Visit #	Visit 1	Visit 2	Visits 3-7	Visit 8	
	Day 0	Week 1	Weeks 2-4	Week 10	
Window		\pm 7 Days	\pm 7 Days	\pm 7 Days	
Informed consent	Х				
Medical History	Х				
Demographics	Х				
MRI Contraindications	х	х	Х		
Concomitant Medications	Х	Х	х	x	x
Inclusion/Exclusion Criteria	х	Х	х		
MMSE	Х				
CDR	Х				
TMS Safety Questionnaire	Х	Х			
Physical Exam	Х				Х
RBANS		Х		Х	
GDS		Х		Х	
iTBS Treatment			Х		
MRI Imaging		Х		Х	
Adverse Events/Serious Adverse Events	Х	Х	Х	Х	x

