5.2 EXCLUSION CRITERIA

An individual who meets any of the following criteria will be excluded from participation in this study:

- 1. Non-AD dementia including, but not limited to, Lewy body dementia, frontotemporal dementia, vascular dementia, Jakob-Creutzfeldt disease, etc.
- 2. Inability to tolerate rs-fMRI
- 3. Contraindication of rs-fMRI due to implants or metal
- 4. Seizure disorder

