7 STUDY INTERVENTION DISCONTINUATION AND PARTICIPANT DISCONTINUATION/WITHDRAWAL

7.1 DISCONTINUATION OF STUDY INTERVENTION

If a clinically significant finding is identified (including, but not limited to changes from baseline) after enrollment, the investigator or qualified designee will determine if any change in participant management is needed. Any new clinically relevant finding will be reported as an adverse event (AE).

If the patient develops a seizure, the PI may discontinue the TMS treatment and early withdrawal procedures will be performed.

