7.2 PARTICIPANT DISCONTINUATION/WITHDRAWAL FROM THE STUDY

Participants are free to withdraw from participation in the study at any time upon request.

An investigator may withdraw a participant from the study if:

- Any medical condition, event or situation occurs such that continued participation in the study would not be in the best interest of the subject.
- The participant meets an exclusion criterion (either newly developed or not previously recognized) that precludes further study participation.
- Significant study procedure non-compliance
- Lost-to-follow up; unable to contact subject

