8.1.2 BASELINE VISIT (VISIT 2) -WEEK 1 (± 7 DAYS)

- Verify inclusion/exclusion criteria
- Neuropsychological battery as mentioned in Section 8.2.
- This visit is at the clinic (HealthPartners Neuroscience Center [NSC]), is about 2 hours. This may be extended depending on availability of Imaging slot.

- Subject will undergo MRI imaging as mentioned in section 8.2
- Subject will be screened for TMS safety
- Review concomitant medications
- Record any adverse or serious adverse events

8.1.3 TREATMENT VISIT (VISTS 3-5 AND VISITS 6,7) (5 DAYS OVER 2 WEEKS, ± 7 DAYS AFTER VISIT 2)

- Verify inclusion/exclusion criteria
- Motor threshold mapping in Visit 3. Visit 3 will be 5 -7 hours. Visits 4-7 will be 4-6 hours each.
- All visits will be at NSC
- Subject will receive 5 theta burst stimulation sessions at each of the treatment visits
- Visits will be on alternating days (weekdays)
- Review concomitant medications at each visit
- Record any adverse or serious adverse events at each visit

8.1.4 FOLLOW-UP/REPEAT VISIT (VISIT 8)(WEEK 10, 6 WEEKS AFTER VISIT 7 ± 7 DAYS)

- Verify inclusion/exclusion criteria
- Neuropsychological battery as mentioned in Section 8.2.
- This visit is at the clinic (HealthPartners Neuroscience Center [NSC]), is about 2 hours. This may be extended depending on availability of Imaging slot.
- Subject will undergo MRI imaging as mentioned in section 8.2
- Review concomitant medications
- Record any adverse or serious adverse events

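### AE/SAE recording ends at withdrawal, so a stimulated participant who leaves early is not assured the six weeks of safety observation that completers get

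*Combined protocol and SAP*

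**What the plan says.** Section 8.4.4 is the only place that sets how long AEs and SAEs are collected. Recording starts at consent and, in its words, "until that person either withdraws or completes study, AEs and SAEs will be recorded". The section's heading mentions follow-up, but its text has no rule for an event still open at that point.

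Section 7.1 says: "If the patient develops a seizure, the PI may discontinue the TMS treatment and early withdrawal procedures will be performed". It does not describe stopping stimulation while staying under scheduled observation. For other clinically significant findings, 7.1 leaves it to the investigator whether anything changes.

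Section 7.2 lists grounds on which an investigator may withdraw a participant. One is: "Any medical condition, event or situation occurs such that continued participation in the study would not be in the best interest of the subject". Another is an exclusion criterion that newly develops, and section 5.2 includes "Seizure disorder" among the exclusions.

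In Table 1 (section 1.3), the row "Adverse Events/Serious Adverse Events" is marked at every visit and in the Early Withdrawal column. That column also marks a physical exam and concomitant medications. It has no day, week or window, and no contact follows it.

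Completers return for Visit 8, which section 8.1.4 places "6 WEEKS AFTER VISIT 7 ± 7 DAYS", and AEs and SAEs are recorded there.

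**The concern.** Read together, these sections make the length of safety observation depend on whether the participant stays in the study. One of the named routes out is a seizure, the most serious TMS risk that section 2.2.3 quantifies. A participant who leaves after stimulation could have a second seizure, a hospitalization or an unresolved event in the following weeks. Nothing in the plan would require it to be recorded.

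What is at stake is the completeness of the safety record. Section 10.1.5 provides no DSMB and relies on a data safety officer who may stop the study if the SAE rate raises concern. An SAE after withdrawal need not enter that rate. Section 2.2.2 says the study is meant to support a larger investigation and a grant application, so its safety record is likely to be reused.

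**Working it through.** The plan states no figure for this window, so there is none to reproduce. The check compares the sections and does date arithmetic on the visit schedule.

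**Inputs**
- Visit 8 is 6 weeks ± 7 days after Visit 7 (section 8.1.4): 42 days, range 42 − 7 = 35 to 42 + 7 = 49.
- There are five treatment visits, three in the first week and two in the second (section 6.1.2). Section 8.1.3 adds: "Visits will be on alternating days (weekdays".
- Assumption: visits fall on Monday, Wednesday, Friday, Monday, Wednesday. Counting d in days from Visit 3, Visits 3 to 7 are at d = 0, 2, 4, 7 and 9.
- Seizure risk is 1/10,000, with no denominator stated (section 2.2.3).
- There are 10 participants and 25 sessions each (sections 5 and 6.1.2), so 10 × 25 = 250 sessions.

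**Observation after the last stimulation**

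Days from the last stimulation to the originally planned Visit 8 = (9 − d) + 42, ± 7.

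| Last stimulated at | d | Assured beyond the early withdrawal check, as written | 6 weeks ± 7 days after last stimulation | To originally planned Visit 8 |
|---|---|---|---|---|
| Visit 3 | 0 | 0 days | 42 (35–49) | 51 (44–58) |
| Visit 4 | 2 | 0 days | 42 (35–49) | 49 (42–56) |
| Visit 5 | 4 | 0 days | 42 (35–49) | 47 (40–54) |
| Visit 6 | 7 | 0 days | 42 (35–49) | 44 (37–51) |
| Visit 7, then leaves | 9 | 0 days | 42 (35–49) | 42 (35–49) |

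The third column counts what the plan assures after the check. Because the check is undated, the interval between the last stimulation and the check is unknown. It could be zero or longer, and someone who leaves partway between Visits 7 and 8 loses only the remainder.

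The last two columns show that two natural anchors differ. For a Visit 3 withdrawal they are 51 − 42 = 9 days apart, so an amendment must name one.

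**Whether another section closes the gap**
- Section 8.5.2 sets 10 working days from when the investigator learns of an unanticipated problem. That is a reporting deadline and requires nobody to look for events.
- The prompt-reporting sentence in 8.4.4 concerns transmission of events, not the collection period.
- The officer's duties listed in 10.1.5 do not extend collection.
- Section 7.3 covers attempts to reach people who miss visits. It provides no safety contact after withdrawal.

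**How often the seizure route might arise**
- If the risk is per person: 1 − (1 − 0.0001)^10 = 0.1%.
- If it is per session: 1 − (1 − 0.0001)^250 = 2.5%.

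The documents give no expected rate for withdrawals of other kinds.

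**The case against.** The best case on the other side is that the gap is narrow.

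- The event that prompts withdrawal occurs before it, so 8.4.4 requires it to be recorded, and Table 1 adds an AE/SAE check and a physical exam. This stands: only later events and outcomes can be lost.
- Only a seizure is explicitly tied to early withdrawal procedures, and there the PI may, not must, stop TMS. Section 7.2 is also permissive. Headache, put at 50% in section 2.2.3, leads to no automatic exit. This stands too. A reader might infer that harmed participants in general get the shortest observation, but the documents do not support that. Most would remain to Visit 8, and people who leave for unrelated reasons are cut off in the same way.
- A reader might infer that a planned harms summary would be biased toward tolerability. Section 9.1.1 plans no such summary, and section 3 lists no safety objective or endpoint, so that inference has no target.
- One truncated record among 10 participants is 10% of the sample, but that is a worst-case share and says nothing about how likely it is.
- Section 2.2.1 says long-term effects are unknown. A six-week window would not settle that, so it is not an argument for this change.
- A qualifying unanticipated problem that becomes known after withdrawal would still be reportable under 8.5.2. Sections 2.2.3 and 10.1.5 defer some safety procedures to separate documents, and the consent pages are not available here. These may mitigate the gap, but none visible in the protocol extends recording.

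What remains is that the recording rule, followed as written, ends observation of exposed people at withdrawal.

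**Conclusion.** The point holds as a gap in safety ascertainment. For a stimulated participant who leaves before Visit 8, the plan assures no AE/SAE recording beyond one undated check, against 35 to 49 days after the last stimulation for completers. The 35 to 49 days come directly from section 8.1.4. The Visit 3 to Visit 6 figures in the last column of the table rest on the assumed weekday pattern.

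Few cases are expected in a study of 10, and the seizure route alone is improbable on the protocol's own risk figure. The gap covers any withdrawal after stimulation, so it is not confined to seizures. It does not alter the primary or exploratory analyses. It warrants correction because missed events can only lower the SAE count on which the data safety officer relies, and because the remedy is small.

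**What to change.** Reconcile sections 7.1 and 8.4.4 with the Early Withdrawal column of Table 1 so that stopping TMS is distinct from leaving the study. In 8.4.4, state that for anyone who received any stimulation, AEs and SAEs are recorded until 6 weeks (± 7 days) after that person's last stimulation, unless consent for further contact or record review is withdrawn. Name that single anchor and do not combine it with the planned Visit 8 date. For completers the two coincide.

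After early withdrawal, collect the information by one telephone contact with participant and caregiver plus a chart review, and add the mark to Table 1. Record the status of any ongoing event at that contact, or at Visit 8 for completers, so that the task has a defined end.

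The cost is a short amendment with IRB review, any matching consent wording, and one call and chart check per early withdrawal. Participants come from the site's own clinic (section 5.5) and caregivers take part in consent (section 8.1.1), so both should be feasible without a clinic visit. The change concerns data collection only. It proposes nothing about how a seizure is managed or when TMS is stopped.

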8.5 UNANTICIPATED PROBLEMS

8.5.1 DEFINITION OF UNANTICIPATED PROBLEMS (UP)

This protocol uses the definition of Unanticipated Problems as defined by the Office for Human Research Protections (OHRP). OHRP considers unanticipated problems involving risks to participants or others to include, in general, any incident, experience, or outcome that meets all of the following criteria:

 Unexpected in terms of nature, severity, or frequency given (a) the research procedures that are described in the protocol-related documents, such as the IRB-approved research protocol and informed consent document; and (b) the characteristics of the participant population being studied;

- 2. Related or possibly related to participation in the research ("possibly related" means there is a reasonable possibility that the incident, experience, or outcome may have been caused by the procedures involved in the research); and
- 3. Suggests that the research places participants or others at a greater risk of harm (including physical, psychological, economic, or social harm) than was previously known or recognized.

8.5.2 UNANTICIPATED PROBLEMS REPORTING

The PI will report unanticipated problems (UPs) to the reviewing IRB. The UP report will include the following information:

- Protocol identifying information: protocol title and number, PI's name, and the IRB project number
- A detailed description of the event, incident, experience, or outcome
- An explanation of the basis for determining that the event, incident, experience, or outcome represents an UP
- A description of any changes to the protocol or other corrective actions that have been taken or are proposed in response to the UP

To satisfy the requirement for prompt reporting, UPs will be reported using the following timeline:

• UPs will be reported to the IRB as soon as possible, but no later than 10 working days after the investigator first learns of the event

9 STATISTICAL CONSIDERATIONS

9.1.1 STATSTICAL PLAN OVERVIEW

The study population demographics (age, race, etc.) will be described using appropriate summary measures (i.e. means, standard deviations, or medians for continuous variables and counts or percentages for discrete variables). Disease characteristics (MMSE and CDR) will also be summarized to describe our population.

The primary aim will be assessed by calculating the difference and corresponding 95% confidence interval between follow-up and baseline connectivity measures of the TGd parcellations. We will conduct a t-test to statistically test if that difference is greater than 0, which would indicate a non-null effect of the TBS intervention on those areas of the brain.

Exploratory aims 1 and 2 will be analyzed similarly to the primary aim.

For exploratory aim 3, parcellations within the DMN, CEN, or SN associated with \geq 4 anomalies on the baseline matrix will be considered for the third TBS treatment. We will descriptively note whether there are shared anomalous parcellations between study patients. If one area of the

brain is anomalous in at least half of the subjects, we will target that area with the third TBS treatment for all patients and analyze it similarly the primary aim. If no such area rises to this level, we will simply describe changes from baseline for the individual areas treated for each patient.

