2.2.3 ASSESSMENT OF POTENTIAL RISKS AND BENEFITS

We believe the potential risks to the participants in this study are minimal.

The following measures will be taken to protect patients from risk of TMS

 Transcranial magnetic stimulation is associated with a 50% risk of self-limiting headache and a 1/10,000 risk of seizures. All patients will undergo the TMS Adult Safety Screen (TASS), which will ensure that the risk of seizure is negligible for each subject participating in the study. In the event of adverse events during TMS treatment, specific procedures will be outlined (aligned with HealthPartners Behavioral Health) and staff will be trained and on-site for any assistance. In addition, all research staff will be

trained on the operation of device (Fried et al., 2020). Repeated exposure to TMS may result in sensorineural hearing loss, which is prevented by routine use of ear plugs.

• Relative to most oral medications used in treatment of dementia, TMS has a very favorable side effect profile.

The following measures will be taken to protect providers and patients from the risk of breach of confidentiality:

- A unique study ID code unrelated to the medical record number or other study subjectspecific information will be assigned to each patient and used to link data from various sources and needed for analysis. The study number will be used on the RedCap database and Infinitome Program. All imaging data uploaded from the NSC research site will be deidentified and uploaded to the Infinitome cloud-based server.
- Infinitome program uses an industrial grade cyber security that is superior to what is
 offered at the leading medical device companies. No personal health information is
 stored on servers and only de-identified scans are stored on a dedicated edge node on
 encrypted MinIO instances. Patient data is only accessed through authenticated calls
 form Kubernetes pods contained in the VPC. The web service requires user
 authentication. Only the data related to a specific facility can be retrieved through
 authenticated calls and are restricted to their use.

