7.3 LOST TO FOLLOW-UP

The reason for participant discontinuation or withdrawal from the study will be recorded on the relevant CRFs. Subjects who sign the informed consent form and undergo only cognitive measures, and not imaging or TMS will not have completed participation and may be replaced.

A participant will be considered lost to follow-up if he or she fails to attend any scheduled study visit and study staff are unable to contact the participant after at least 5 attempts.

The following actions must be taken if a participant fails to attend any required study visit:

- Study staff will attempt to contact the participant, reschedule the missed visit, counsel the participant on the importance of maintaining the assigned visit schedule and ascertain if the participant wishes to and/or should continue in the study.
- Before a participant is deemed lost to follow-up, the investigator or designee will make every effort to regain contact with the participant (where possible, telephone calls or e-mail – if no answer leave a voicemail on the first and last attempt). These contact attempts will be documented.
- Should the participant continue to be unreachable, he or she will be considered to have withdrawn from the study with a primary reason of lost to follow-up.

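### A treated participant who is withdrawn early has no follow-up MRI, RBANS or GDS scheduled, so by default the before-after change is estimated only in those who stayed

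*Combined protocol and SAP*

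**What the plan says.** Section 9.1.1 assesses the primary aim by "calculating the difference and corresponding 95% confidence interval between follow-up and baseline connectivity measures of the TGd parcellations", with a t-test on the difference. RBANS and GDS are handled in the same way. Section 9 names no analysis set and no method for missing follow-up data.

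Table 1 (section 1.3) marks MRI, RBANS and GDS at Baseline and Visit 8 only. Its "Early Withdrawal" column marks concomitant medications, physical exam and adverse events.

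Three parts of section 7 bear on who reaches Visit 8:

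- 7.1: after a seizure, "the PI may discontinue the TMS treatment and early withdrawal procedures will be performed".
- 7.2: the investigator may withdraw a participant on several grounds, one being "Any medical condition, event or situation occurs such that continued participation in the study would not be in the best interest of the subject".
- 7.3: replacement is offered for subjects who "undergo only cognitive measures, and not imaging or TMS will not have completed participation and may be replaced". Anyone who has started iTBS falls outside that rule. The same section says "The reason for participant discontinuation or withdrawal from the study will be recorded on the relevant CRFs".

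Section 8.1.4 dates Visit 8 as "WEEK 10, 6 WEEKS AFTER VISIT 7", with a 7-day window. Section 9.1.2 claims 80% power with 10 subjects, the same 10 to be enrolled under section 5, with no allowance for loss.

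**The concern.** A change from baseline cannot be computed without the second scan. The schedule gives an early-withdrawn participant safety checks and no outcome assessment. Someone who stops before Visit 7 also has no Visit 7 from which to count six weeks, and nothing says they should come at Week 10 instead.

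Withdrawal for a medical event or poor tolerance may be related to how a person takes up to 18,000 pulses a day. If those people would also have changed less, the estimate in those who stayed is too favourable. A scan that was not taken cannot be recovered at analysis. Section 2.2.2 says the study is to support a grant application and work in a larger cohort, so a change seen only in those who stayed could be carried into the planning of that next study.

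**Working it through.** **1. The plan's own figure.** Inputs from 9.1.2: n = 10, change 0.033, SD 0.033, so the standardised change is 0.033/0.033 = 1. Alpha is not stated. A paired t-test at two-sided 0.05 (noncentral t, 9 degrees of freedom, noncentrality 1 × √10 = 3.16) gives power 0.803, which reproduces the 80%. One-sided 0.05 gives 0.898, which does not.

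**2. Following one participant through the text.** Suppose iTBS is stopped at Visit 4 and the participant is withdrawn. Table 1 gives medications, physical exam and adverse events. Visit 8 is six weeks after a Visit 7 that did not take place. Replacement under 7.3 does not apply. The participant has a baseline scan and no follow-up scan, and drops out of a t-test on the change.

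**3. How likely a loss is.** The documents give no withdrawal rate, so the rates below are assumptions. With Binomial(10, p):

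| Assumed p | P(at least 1 lost) = 1 − (1 − p)^10 | P(at least 2 lost) |
|---|---|---|
| 5% | 40% | 9% |
| 10% | 65% | 26% |
| 20% | 89% | 62% |

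Seizure is an unlikely route. Section 2.2.3 gives "a 50% risk of self-limiting headache and a 1/10,000 risk of seizures". If the seizure figure is per participant, the chance of any seizure is 1 − 0.9999^10 = 0.1%. If it is per session (25 × 10 = 250 sessions), it is 1 − 0.9999^250 = 2.5%. General intolerance or an unrelated medical event is more likely.

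**4. Shift in the estimate.** Let d be the mean change in those who stayed minus the mean change that those withdrawn would have had. Leaving out k of 10 shifts the estimate by (k/10) × d. The 95% CI half-width is t(0.975, n − 1) × 0.033/√n, which is 0.0236 for 10 pairs, 0.0254 for 9 and 0.0276 for 8. The range of d from 0 to 0.033 is an assumption.

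- k = 1: shift 0 to 0.0033, at most 0.0033/0.0254 = 13% of the half-width.
- k = 2: shift 0 to 0.0066, at most 0.0066/0.0276 = 24% of the half-width.

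**5. Power with fewer pairs.** If 0.033 is the SD of the change and the test is two-sided at 0.05, power is 74.8% with 9 pairs and 68.1% with 8. One-sided at 0.05, it is 86.2% and 81.5%. Section 9.1.2 describes 0.033 as a pooled SD of connectivity levels. If it is the SD of levels between people, the SD of the change is 0.033 × √(2(1 − ρ)), where ρ is the baseline to follow-up correlation. Power with all 10 pairs (two-sided 0.05) is then:

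| Assumed ρ | SD of change | Power |
|---|---|---|
| 0.25 | 0.0404 | 63.4% |
| 0.5 | 0.033 | 80.3% |
| 0.75 | 0.0233 | 97.7% |

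Uncertainty about the SD matters more to power than the loss of one or two scans.

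**The case against.** The strongest case against is that the harm is small and its inputs are assumed. No withdrawal rate is given, and nothing in the documents links poor tolerance to change in TGd connectivity. Much of the loss is also beyond repair: participants who cannot be contacted, withdraw consent or can no longer have an MRI will not be scanned whatever the protocol says. Section 7.3 already requires staff to try to reschedule a missed visit, section 5.5 ties payment to completing all visits, and Week 10 is printed beside the six-week rule. Scans from people who stopped early would reflect a partial dose and a longer gap since the last stimulation.

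All of this limits the size of the point. It does not remove it, because the rescheduling rule concerns missed visits and the schedule itself leaves the outcomes out for someone who has been withdrawn.

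A reader might infer more than the text supports:

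- That those who stop iTBS are barred from Visit 8. They are not. A participant who stops but stays enrolled may attend; the text does not say that they should.
- That the plan prescribes an analysis of completers. It is silent, and that analysis is only the default of a t-test on the change.
- That withdrawals go unrecorded. Section 7.3 records the reasons, and 8.4.4 records adverse events until withdrawal or completion.
- That the 80% is wrong, or will fall to 74.8% or 68.1%. The 80% reproduces for 10 pairs, and the lower figures need both a two-sided test and 0.033 as the SD of the change.

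**Conclusion.** The point holds as a gap in outcome collection for treated participants who are withdrawn early. It follows from the stated schedule and from 7.1, together with the timing of Visit 8. The resulting shift would be modest: at most 0.0033 with one of ten lost and 0.0066 with two, if the difference in change is no more than 0.033. It would run upward only if those withdrawn respond less, which the documents do not show. How often it would arise is unknown. A claim of serious bias, or of a failed power calculation, would go beyond the documents. The change is worth making because it is cheap and a missed scan cannot be obtained later.

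**What to change.** 1. **7.1.** Separate stopping iTBS from leaving the study. Replace the seizure sentence so that the participant has the early withdrawal safety procedures and, like anyone who stops iTBS for another reason, is asked to attend Visit 8 at Week 10 (± 7 days) unless consent is withdrawn, MRI is contraindicated, or the investigator judges it not in their interest. Adding a retention sentence beside the present one would leave the two in conflict.
2. **8.1.4.** State that Week 10 applies to those who did not reach Visit 7.
3. **Table 1.** Add MRI, RBANS and GDS at early withdrawal for treated participants who are willing but cannot attend Visit 8.
4. **9.1.1.** State that the primary analysis includes all treated participants with a baseline and a Visit 8 scan. Add two sensitivity analyses: one restricted to those who completed iTBS, and one adding the early-withdrawal scans.
5. **9.1.2.** Say only that 80% refers to 10 evaluable pairs and assumes that 0.033 is the SD of the change. Do not insert fixed power figures for 9 and 8 pairs.

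Wider replacement would not do the same job: it restores the number but not the missing outcomes.

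The cost is text changes in five places and at most one MRI, RBANS and GDS per early stopper, in place of that person's Visit 8. Some data will come from a partial dose or fall off schedule, which the sensitivity analyses address. No participants are added, and no new field is needed for the reason for withdrawal.
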